# **Effect of Vanilla on Hypoxic Intermittent Events in Premature Infants**

**NCT02630147**

**Protocol version 1.0**

**April 13, 2015**

## 1. OBJECTIVES AND HYPOTHESIS

### 1.1. Main objective

The main objective of the study is to assess whether exposure to vanilla odor decreases the number of intermittent hypoxia events in preterm infants born between 32 and 33 weeks and reaching near term-equivalent age. A hypoxic event is defined as a desaturation < 90% with a decrease in oxygen saturation ( $\text{SpO}_2$ )  $\geq 5\%$  compared to preceding  $\text{SpO}_2$ , for a duration  $\geq 5$  seconds (Rhein et al. 2014).

### 1.2. Secondary objectives

Secondary objectives are to determine the effect of vanilla odor further by measuring the percentage of recording time spent with a  $\text{SpO}_2 < 80\%$ , the percentage of recording time spent with a  $\text{SpO}_2 < 90\%$ , the bradycardia index (number per hour), the percentage of recording time spent in periodic breathing, as well as the effect on heart and respiratory rate variability. In addition, we aim to gather preliminary results on the effect of vanilla odor on the states of alertness.

### 1.3. Hypothesis

We hypothesize that vanilla odor stimulates the cardiorespiratory centers, and especially decreases periodic breathing and arterial oxygenation oscillations in preterm infants at near-term-equivalent age.

## 2. METHODS

### 2.1. Study design

To fulfill our main objective, a randomized, controlled, unblinded, balanced cross-over study will be performed.

### 2.2. Study population and patient sample

The study population will be preterm infants born between 32 and 33 weeks and hospitalized in the neonatal care unit at the University of Sherbrooke Hospital Center, with a postnatal age of 3 to 4 weeks, i.e., close to a term-equivalent age.

#### 2.2.1. Patient sample

We will study a convenience sample. Preterm infants in the neonatal care unit will be included in chronological order of their birth.

The sample size has been computed with the help of [name], biostatistician at the University of Sherbrooke Hospital Research Center using the *nQuery* software. Literature data suggest that an average of 4 periodic breathing epochs per hour is expected in the population under study (Martin et al, 2011). A sample of 17 patients is therefore necessary to detect a difference of 33% between conditions, with a power of 80% and an  $\alpha$  error of 0.05. Accordingly, we aim to include 30 preterm infants to get 20 technically valid recordings. If necessary, we will continue patient recruitment to reach 20 valid recordings. We believe that the latter can be obtained within a 2-year period. This number is based on data from the neonatal care unit at the University of Sherbrooke Hospital Center showing that 51 and 59 preterm infants were born between 32 and 33 weeks in 2012 and 2013 respectively.

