### **2.6. Data analysis**

#### **2.6.1. Variables**

In agreement with our main research question, we will compute the 90% and 80% desaturation indices per hour from the two 12-hour nocturnal recordings. We will also compute the percentage of the recording time spent with  $\text{SpO}_2 < 80\%$ , the percentage of the recording time spent with  $\text{SpO}_2 < 90\%$ , the percentage of the recording time spent in periodic breathing and the bradycardia index per hour.

Finally, a corollary study will be performed by a physiology doctoral student under the direction of [name] to assess the effect of vanilla odor on heart and respiratory rate variability. This assessment will be performed on the 12-hour recordings and will not require any additional intervention on the preterm infants.

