### **2.6.2. Definitions**

- States of alertness: the usual electrophysiological and behavioral criteria will be used to recognize wakefulness, NREM and REM sleep (Anders et al, 1984; Grigg-Damberger M et al, 2007).
- Central apneas will be defined by the absence of both nasal airflow and respiratory movements for at least two respiratory cycles, if a desaturation  $\geq 3\%$  or an arousal is present, or for 20 seconds in the absence of desaturation or arousal (Nunez J et al, 2011; Henderson-Smart DJ et al, 1986).
- Periodic breathing: an epoch of periodic breathing will be defined by the presence of at least three central apneas with a duration  $\geq 3$  seconds, with a maximum of 20 seconds of normal respiration between two apneas (Brockmann PE et al, 2013).
- Desaturation: a desaturation will be defined as a decrease in  $\text{SpO}_2$  below 90% and of at least 5% compared to the preceding  $\text{SpO}_2$ , for a duration  $> 5$  seconds (Rhein et al, 2014).
- Bradycardia: a bradycardia will be defined as a decrease of at least 33% in heart rate for  $\geq 5$  seconds (Poets et al, 1993).

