### **2.7. Statistical analysis**

Statistical analysis of the results has been elaborated with [name], biostatistician at the University of Sherbrooke Hospital Research Center. For each continuous quantitative variable, the normality of the distribution will be first confirmed with the *Shapiro-Wilks* test. Then, a mixed model will be designed with the SPSS software and used under close supervision of [name].

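### The only power calculation is for periodic-breathing epochs per hour, not for the primary outcome (hypoxic events), and it gives no SD, so the 80% power is unsupported for the main question

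*Combined protocol and SAP*

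**What the plan says.** Section 1.1 sets the main objective: to "assess whether exposure to vanilla odor decreases the number of intermittent hypoxia events in preterm infants". Section 2.6.1 names the variables for it: "In agreement with our main research question, we will compute the 90% and 80% desaturation indices per hour", taken from the two 12-hour night recordings.

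Section 2.2.1 holds the only sample-size reasoning. Its starting point is "Literature data suggest that an average of 4 periodic breathing epochs per hour is expected in the population under study", and its result is "A sample of 17 patients is therefore necessary to detect a difference of 33% between conditions, with a power of 80" per cent and an alpha of 0.05. It then plans to include 30 infants to obtain 20 valid recordings, and to keep recruiting until there are 20.

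Periodic breathing appears in three other places:

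- The hypothesis (1.3) is that vanilla "especially decreases periodic breathing and arterial oxygenation oscillations in preterm infants".
- It is a secondary outcome (1.2, repeated in 2.6.1), measured as "the percentage of recording time spent in periodic breathing".
- Section 2.6.2 gives a definition: "an epoch of periodic breathing will be defined by the presence of at least three central apneas".

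On the analysis, section 2.7 says that "a mixed model will be designed with the SPSS software", without listing its terms.

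**The concern.** There are two separate defects.

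1. **The variable.** By the protocol's own definitions, a desaturation is an SpO2 event and an epoch of periodic breathing is a run of central apneas. Nothing in the document converts one rate to the other. Epochs per hour is not even a planned outcome, because periodic breathing is to be analysed as a share of recording time. The power figure therefore belongs to neither the primary outcome nor any secondary outcome as measured.

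2. **The derivation.** In a within-infant comparison, a mean rate, a relative difference, a power and an alpha do not determine a sample size. The SD of the within-infant difference is also needed, together with the test and its sidedness. None of these is stated, so 17 does not follow from what precedes it.

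At stake is the only justification for the number of infants studied. If the desaturation index shows no difference, the protocol offers no stated detectable difference in that index against which to read the result.

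**Working it through.** **Inputs from section 2.2.1.** Mean 4 per hour; difference 33%, read as relative, so 0.33 × 4 = 1.32 per hour; power 80%; alpha 0.05; 17 patients computed; 20 valid recordings targeted. Section 2.1 gives the design as a balanced cross-over. The SD is not given anywhere.

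**Method.** Paired t-test with the noncentral t distribution, as an approximation to the unspecified mixed model. With d = (difference) / (SD of the within-infant difference), power = P(|T| > t critical), where T has n − 1 degrees of freedom and noncentrality d√n. The test is taken as two-sided unless stated.

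**Step 1: can 17 be reproduced?** Not from the stated inputs, so I solved for the SD that would return it. The d detectable with 80% power is 0.749 at n = 16 and 0.724 at n = 17. For 17 to be the smallest adequate n, the SD must lie between:

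- 0.33 / 0.749 = 0.440 of the mean, i.e. 1.76 per hour at a mean of 4; and
- 0.33 / 0.724 = 0.456 of the mean, i.e. 1.82 per hour.

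This window depends on the test. A one-sided t-test moves it to 0.506 to 0.524 of the mean. The two-sided normal approximation, n = (SD × (1.960 + 0.842) / 1.32)², moves it to about 1.88 to 1.94 per hour (47% to 49%). So 17 is attainable with an SD somewhat below or near 2 per hour, but the text does not show which assumption was used.

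**Step 2: what does the target of 20 add?** The detectable d at n = 20 is 0.660. At the d implied by n = 17 (0.724), 20 complete pairs give 87% power. For a 33% reduction, 80% power holds up to an SD of 0.33 / 0.660 = 0.50 of the mean.

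**Step 3: power for the desaturation index.** The documents give neither its baseline rate nor its SD. The first column below is therefore an assumed range, and no row is more likely than another on the documents' evidence. The first four columns refer to a 33% reduction; the last gives the reduction that 20 pairs detect with 80% power, which is 0.660 × the SD.

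| SD of difference / mean | Power, 17 pairs | Power, 20 pairs | Pairs for 80% power | Reduction detectable, 20 pairs |
|---|---|---|---|---|
| 30% | 99% | >99% | 9 | 20% |
| 40% | 89% | 94% | 14 | 26% |
| 50% | 72% | 80% | 21 | 33% |
| 60% | 57% | 65% | 28 | 40% |
| 75% | 40% | 46% | 43 | 50% |
| 100% | 25% | 29% | 75 | 66% |

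In the 50% row, power with 20 pairs is 79.95%. It rounds to 80%, but strictly 21 pairs are needed.

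**The case against.** **It may be a slip.** The reference cited for the rate of 4 per hour has a title about intermittent hypoxic episodes, and events per hour is the unit of the desaturation index, not of the periodic-breathing outcome. If hypoxic episodes were meant, the mismatch shrinks to a wording error. This is plausible, but the document cannot settle it. On that reading the text still names the wrong variable in the key input, and the missing SD still leaves 17 unverifiable.

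**Periodic breathing is in the hypothesis.** It is, but beside oxygenation oscillations, and section 2.1 ties the design to the main objective, which is hypoxic events.

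**The calculation was run by a biostatistician in named software, and 20 exceeds 17.** The absence of an SD on paper does not show that none was used; that point stands. But neither the software nor its user supplies the missing value to a reader, and the margin from 17 to 20 protects only up to an SD of about half the mean.

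**A null result can be read from its confidence interval.** This also stands: the type I error and the validity of the comparison are untouched. What is lost is narrower, namely a difference in the primary outcome, stated in advance, that the trial was designed to detect.

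**The numerical range is assumed and the window depends on the test.** Both are true, and for that reason the low power figures are not evidence that the trial is too small.

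**Conclusion.** The concern holds and should be corrected. As written, the 80% power is attached to a variable that is neither the primary outcome nor a listed outcome, and the figure of 17 does not follow from the inputs given. Power for the desaturation index is unknown rather than shown to be low. With 20 complete pairs it is adequate for a 33% reduction if the SD of the within-infant difference is up to about 50% of the mean, and inadequate above that. These figures rest on a two-sided paired t-test standing in for the mixed model, on reading 33% as a relative difference, and on an assumed range of SDs. The mismatch itself and the absence of an SD are plain from the text and need none of these assumptions.

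**What to change.** In section 2.2.1:

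1. If hypoxic events were meant, replace the periodic-breathing variable with the primary outcome. If not, redo the calculation for the 90% desaturation index per hour, the index that matches the event definition in section 1.1.
2. In either case state the mean, the SD of the within-infant difference, the test and the sidedness. Suggested wording:

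> Assuming a control mean of [m]/h and an SD of the within-infant difference of [s]/h, [n] infants with both nights valid give 80% power for a 33% reduction in the 90% desaturation index (paired t-test, two-sided alpha 0.05).

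3. If no SD can be found, withdraw the 80% claim for the primary outcome and write:

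> 20 infants with both nights valid give 80% power to detect 0.66 SD of the within-infant difference (two-sided alpha 0.05).

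This fallback is honest but says nothing about events per hour, so option 2 is better wherever an SD is available.

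A small clarification belongs in the same edit: word the target as 20 infants with both 12-hour recordings technically valid, since the power depends on complete pairs.

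**Cost.** Protocol wording and one recalculation. The stated power may become less favourable. No extra enrolment follows from the correction itself, because the claim can be withdrawn. If the sponsor prefers to keep 80% power for a 33% reduction, the pairs needed range from 9 to 75 over the assumed SDs, so 20 could prove more than enough or too few.

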##### 2.2.1.1. Inclusion criteria

- Birth between 32 and 33 weeks of gestational age
- Postnatal age between 3 and 4 weeks
- Absence of any respiratory support or supplemental oxygen
- Clinically stable for a minimum of 48 hours prior to inclusion
- Obtention of parental consent.

##### 2.2.1.2. Exclusion criteria:

- Any respiratory condition (e.g., pneumonia or bronchopulmonary dysplasia) other than apnea of prematurity
- Intraventricular hemorrhage grade 3 or 4, or periventricular leukomalacia;
- Chromosomal anomalies
- Congenital malformation susceptible to lead to cardiorespiratory or neurological complications

- Parental refusal
- Significant clinical deterioration during the study period.

\* Note that caffeine treatment is not an exclusion criterion.

### **2.3. Measuring instruments**

Our polysomnography equipment will allow recording electrocardiographic activity (ECG), SpO2 (Masimo oximeter), and thoracic and abdominal respiratory movements (respiratory inductance plethysmography, *Resptrace*). Preliminary observations will be collected for electroencephalographic activity and eye movements (states of alertness). No invasive sensor will be used for the study.

### **2.4. Vanilla odorization**

As reported in past studies by Marlier L et al (2005), and Edraki M et al (2013), we will use 2 mL of a 2% vanillin solution to odorize the infant environment. The vanilla solution will be spread on the infant's bib, both on the shoulders and the superior part of the thorax. According to results from the two past studies cited above, a single application at the beginning of the study will be sufficient. Following recordings, we will retrospectively check in the infant's medical record whether any unexpected event has occurred during and within 24 hours after the odorization period, to detect any side-effect potentially related to vanilla odor exposure.

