### **2.5. Conduct of the study**

#### **2.5.1. Data collection**

Following patient recruitment, medical history taking, and physical examination, all included preterm infants will undergo two nocturnal continuous recordings of ECG, SpO2 and respiratory movements between 9:00 pm and 9:00 am. The two 12-hour recordings will be performed at 48-hour interval—i.e., with a 24-hour wash-out period—, one in the control condition, and the other under vanilla odor exposure, in a random order and in a balanced fashion.

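### The chart check for side effects covers only the vanilla period and the 24 hours after it, so events outside the overnight recordings have no control-night comparator

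*Combined protocol and SAP*

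**What the plan says.** Section 2.4 contains the only safety provision in the document. It is retrospective and based on records: "Following recordings, we will retrospectively check in the infant's medical record". The period searched is tied to exposure, namely "whether any unexpected event has occurred during and within 24 hours after the odorization period", and the purpose is "to detect any side-effect potentially related to vanilla odor exposure". What counts as an unexpected event is not defined.

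Section 2.5.1 gives each infant two nights, "one in the control condition, and the other under vanilla odor exposure, in a random order and in a balanced fashion". Neither that section nor any other describes a chart check around the control night. Sections 2.6.1 (variables) and 2.7 (statistical analysis) do not list or compare unexpected events by condition. Section 2.1 states that the study is unblinded. Section 2.2.1.2 lists clinical deterioration during the study among the exclusion criteria, not among the outcomes.

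**The concern.** To judge whether a charted event may be due to vanilla, one needs some idea of how often such events occur in the same infants without it. These are hospitalised preterm infants in whom apnea of prematurity and caffeine treatment are allowed (section 2.2.1.2), so some events without vanilla are plausible. The cross-over supplies a comparator within each infant, but the safety check does not use it.

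The gap is limited to two kinds of event: charted events that the overnight signals do not capture, and events in the 24 hours after recording. For these, the investigators would have a count from the vanilla window alone, read by people who may know the condition and without a definition of what to count. An isolated event could be wrongly put down to vanilla or wrongly dismissed as background.

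**Working it through.** The plan states no safety figure, so there is none to reproduce. Three things can be checked.

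**1. Can the control night serve as a comparator?** Recordings run "between 9:00 pm and 9:00 am" (12 h), and section 2.5.1 says "The two 12-hour recordings will be performed at 48-hour interval". I take the 48 h as start to start, because both nights begin at 9 pm.

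- Length of each window: 12 h recording + 24 h after = 36 h.
- First window: 9 pm on day 1 to 9 am on day 3.
- Second recording starts: 9 pm on day 3, which is 48 − 36 = 12 h after the first window closes.

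The windows do not overlap in either order, so each infant can be its own control. If the odorization period were taken to include the 3-hour morning polysomnography done in some infants (section 2.5.2), the window would be 12 + 3 + 24 = 39 h, still 48 − 39 = 9 h clear of the second recording.

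Of the 36 h, 24 h (two thirds) lie outside the overnight recording.

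**2. How likely is an event in the vanilla window if vanilla does nothing?** Inputs:

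- Number of infants n: 20 (the target for valid recordings) or 30 (the planned inclusions), both from section 2.2.1.
- Background probability p that an infant has at least one unexpected charted event in a 36-h window: not in the document. I assume 2% to 20%, equal and independent across infants.

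Formulas: expected affected infants = n × p; chance of at least one = 1 − (1 − p)^n. For example, with n = 20 and p = 0.05: 20 × 0.05 = 1, and 1 − 0.95^20 = 0.642.

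| Assumed p | n = 20: expected | n = 20: chance of ≥1 | n = 30: expected | n = 30: chance of ≥1 |
|---|---|---|---|---|
| 2% | 0.4 | 33% | 0.6 | 45% |
| 5% | 1.0 | 64% | 1.5 | 79% |
| 10% | 2.0 | 88% | 3.0 | 96% |
| 20% | 4.0 | 99% | 6.0 | 99.9% |

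From an assumed 5% upward, at least one event needing interpretation is more likely than not, with no vanilla effect at all.

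If no event is seen, the vanilla window is still informative alone. The one-sided 95% upper limit on the event probability is 1 − 0.05^(1/n): 13.9% for n = 20 and 9.5% for n = 30.

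**3. What could a paired comparison show?** In an exact sign (McNemar) test with k discordant infants, all in the same direction, the two-sided p-value is 2 × 0.5^k. For k = 5 it is 0.0625; for k = 6 it is 0.031. At least six discordant infants, all in one direction, are therefore needed for p < 0.05. With 20 to 30 infants the table would be descriptive.

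**The case against.** The strongest reply is that the events most typical of prematurity are already compared. ECG, SpO2 and respiratory movements are recorded on both nights (section 2.5.1), and section 2.6.1 derives desaturation indices, time below the saturation thresholds, periodic breathing and a bradycardia index. That comparison is within-infant and more objective than a chart. The polysomnography subsample also has some hours recorded after each night. This stands. A reader might infer from section 2.4 that background events of prematurity cannot be told apart from vanilla effects at all. The document does not support that for cardiorespiratory events during the recorded hours.

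Second, section 2.4 promises detection, not a comparison. Safety is not an objective in sections 1.1 or 1.2, nor an analysis in section 2.7, and looking in the exposed window does serve detection. A reader might infer that no safety conclusion is possible in either direction. That goes too far: the plan makes no comparative safety claim, zero events would still bound the rate, and a single event can be assessed from its timing and context. But the check is aimed at events potentially related to vanilla, and that judgement is where a comparator helps.

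Third, the background rates are assumptions. Infants must be stable for 48 hours and free of respiratory support (section 2.2.1.1), and usual apnea could be read as expected. This argues for caution about the upper end of the range. Even at 2%, though, the chance of at least one event is 33% to 45%.

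Fourth, the control window could be reviewed later, since the check is retrospective, and the gap does not touch the primary analysis. Both are true, and they limit how serious the point is. Specifying both windows in advance avoids deciding to look at the control chart only after an event has appeared under vanilla.

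**Conclusion.** The point holds in a limited form. The check is one-sided as written, in an unblinded study whose design already supplies a control window that does not overlap the vanilla window. The missing comparator affects charted events that the overnight signals do not capture, and events in the 24 hours after recording. Under an assumed background of 2% to 20% per 36-hour window and no vanilla effect, the chance of having at least one affected infant to interpret is 33% to 99% for n = 20 and 45% to 99.9% for n = 30. These figures rest entirely on the assumed rate and on independence between infants. The main efficacy analysis is unaffected. This is a cheap improvement, not a flaw that undermines the trial.

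**What to change.** In section 2.4, apply the identical retrospective chart check to the control recording and the 24 hours after it, using one event list fixed in advance for both windows. Where practical, have the record read by someone unaware of which night was which.

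Report events by condition as a descriptive paired table for all infants exposed, including any later excluded for deterioration or without a valid recording. Section 2.4 does not restrict the check to valid recordings, but the exclusion criterion could remove affected infants from the report unless this is stated. List infants with only one window separately by condition, including any who leave after a control night, so that neither column is selectively trimmed.

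The cost is one more brief review per infant, about 20 to 30 in all (more if recruitment is extended), of records already being opened. No study procedure changes. The comparison will be descriptive and should be labelled so.
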